13.3.2 Supportive Analysis Methods for Secondary Efficacy Endpoints

The FVIII activity level will be summarized descriptively in 4 or 6-week visit windows with missing data imputed from baseline up to the last possible visit by the data cut-off for the 2-year analysis (eg. if a subject was lost to follow-up at Week 60 and would have been followed for 104 weeks by the data cut-off, his FVIII activity levels beyond Week 60 will be imputed to be 0 IU/dL up to Week 104). The visits and visit windows are defined in Appendix 20.1 Visit Windows. Each subject's FVIII activity level in a visit window is defined as the median of the values obtained during the window. The number and proportion of subjects achieving FVIII activity level per chromogenic assay of <LLoQ (3 IU/dL), between levels of \geq LLoQ (3 IU/dL)-<5 IU/dL, between the levels of \geq 5-<15 IU/dL, between the levels of \geq 15-<40 IU/dL, between the levels of \geq 40-<=150 IU/dL, and >150 IU/dL will also be summarized every 4 or 6 weeks from baseline up to data cut-off. The number and proportion of subjects whose FVIII activity is <5, \geq 5-<40 and \geq 40 IU/dL will also be provided.

Boxplots of median FVIII activity values using chromogenic substrate assay at 4-week or 6-week windows (Appendix 20.1 Visit Windows) over time will be provided.

The by 4 or 6-week analysis will be repeated using efficacy evaluation period for supportive analysis of FVIII activity without imputation for mITT population.

The maximum of each subject's FVIII activity levels (medians of the values in visit windows defined in Appendix 20.1), and the time to the maximum level, will be summarized descriptively. The number and proportion of subjects whose maximum FVIII activity level is < LLoQ (3 IU/dL), between levels of \geq LLoQ (3 IU/dL)-<5 IU/dL, between the levels of \geq 5-<15 IU/dL, between the levels of \geq 15-<40 IU/dL, between the levels of \geq 40-<=150 IU/dL, and >150 IU/dL will also be summarized.

The primary and supportive analyses described above may be conducted for FVIII activity values by one-stage clotting assay.

**Study 270-301 Statistical Analysis Plan**

To investigate the relationship between the FVIII activity values by one-stage clotting and chromogenic substrate assays, a linear regression to fit a line to the observed values by these two assays will be conducted for the mITT population.

For long-term FVIII activity data, the overall trend will be examined. The FVIII activity levels, their changes from baseline, will be summarized descriptively at milestone timepoints defined as the end of every 6 months post-BMN 270 infusion (eg, Weeks 23-26, Weeks 49-52, Week 76 and 104 with the visit windows defined in Appendix 20.1). Missing data will be imputed using the imputation methods specified in Section 5.6. In addition, proportion of subjects whose FVIII level is < LLoQ (3 IU/dL), between levels of \geq LLoQ (3 IU/dL) - < 5 IU/dL, between the levels of \geq 5 - < 15 IU/dL, between the levels of \geq 15 - < 40 IU/dL, between the levels of \geq 40 - \leq 150 IU/dL, and > 150 IU/dL will be summarized. The change in FVIII activity between certain milestone timepoints (eg, between Weeks 23-26 and Weeks 49-52, between Weeks 49-52 and Week 76, between Week 76 and Week 104) and between Week 104 and the maximal FVIII activity by the Week 104 will also be summarized. In addition, LOESS (locally estimated scatterplot smoothing) curves of FVIII activity will be generated to show the overall trend, to compare trends between directly enrolled subjects and Study 270-902 rollover subjects, and to compare trends observed in Study 270-301 with those observed in 4E13 and 6E13 vg/kg cohorts of the Phase 2 Study 270-201.

Exploratory analyses including univariate and multiple logistic regression may be performed to evaluate associations between demographic and baseline characteristics and other parameters and FVIII activity at Week 104 to assess potential predictors of variability.

Total and annualized FVIII utilization (IU/kg/year) will be listed by subject and by periods (pre-BMN 270 infusion [baseline period], Weeks 1-4, Week 1 to end of original FVIII prophylaxis, Post FVIII Prophylaxis-52, Weeks 53-104, and the efficacy evaluation periods as defined in Table 13.1.1), and the annualized utilization rates will be summarized descriptively.

The analysis for the change from baseline in the annualized utilization (IU/kg/year) of exogenous FVIII replacement therapy will be conducted using data in the efficacy evaluation periods as defined in Table 13.1.1.

Assessments of exogenous FVIII dosing and management of bleeding or peri-operative bleeding will be summarized descriptively for the mITT population.

The analyses for the change from baseline in ABR for all bleeds will be similar as the analyses for the ABR for treated bleeds.

**Study 270-301 Statistical Analysis Plan**

The Haemo-QoL-A Total score will be summarized descriptively by visits. A graphical summary of mean change over time will be provided.

The analyses for Haemo-QoL-A domain scores (Physical functioning, Consequence of bleeding, Role functioning) will be the same as the Total score analyses.

13.3.3 Sensitivity Analysis Methods for Secondary Efficacy Endpoints

A one-sample t-test of the change from baseline to Week 104 in FVIII activity using observed cases will be performed as a sensitivity analysis.

The primary analysis for the change from baseline to Week 104 in FVIII activity using LOCF approach will be performed. Similarly, the primary analysis with imputing missing data at Week 104 to be 0 IU/dL will be performed.

The primary analysis for the change from baseline to Week 104 in FVIII activity will be conducted for the PP population when applicable.

To investigate the robustness of the primary analysis, which uses the median FVIII activity value if more than one assessment falls within an analysis window, a sensitivity analysis may be performed using the mean of the multiple assessments. This sensitivity analysis will be based on the mITT population with the same imputation strategy as the primary analysis.

A mixed model for repeated measures (MMRM) approach will also be used on the observed cases on the mITT population as an alternative approach to evaluate the impact of missing data assuming missing at random. The model will include visit (every 4 weeks, from baseline to Week 104) as the only factor and will use an unstructured covariance matrix. The least squares (LS) mean change from baseline to Week 104 will be reported.

The following sensitivity analyses for the change from baseline in the annualized utilization (IU/kg/year) of exogenous FVIII replacement therapy will be performed:

- The primary analysis will be performed on the PP population when applicable.
- The primary analysis will be performed with baseline (prior to BMN 270 infusion while receiving FVIII prophylaxis) values calculated using the data 12-months prior to study enrollment

The Haemo-QoL-A Total score will be analyzed using an MMRM approach. The model will include visit (baseline, Week 4, Week 12, Week 26, Week 52, Week 76, Week 104) as the only factor and will use an unstructured covariance matrix. The LS mean change from baseline to Week 104 will be reported.

The analyses for Haemo-QoL-A domain scores (Physical functioning, Consequence of bleeding, Role functioning) will be the same as the Total score analyses.

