- The change from baseline in the ABR in the efficacy evaluation period (“Post FVIII Prophylaxis to Last Visit”) will also be tested using Wilcoxon signed-rank test.
- If a subject restarts FVIII prophylaxis, starts emicizumab, or discontinues from the study prior to the data cut-off for the analysis, a sensitivity analysis will be performed where the post-baseline ABR for treated bleeds is imputed as the same as the baseline ABR for treated bleeds (ie, the change in ABR for treated bleeds is 0).

Secondary efficacy endpoints and analyses:

The secondary endpoints are:

- The change from baseline (assuming no treatment for severe hemophilia A) in FVIII activity, as measured by chromogenic substrate assay, at Week 104 post-BMN 270 infusion

Study 270-301 Statistical Analysis Plan

- The change from baseline (prior to BMN 270 infusion while receiving FVIII prophylaxis) in the annualized utilization (IU/kg/year) of exogenous FVIII replacement therapy in the efficacy evaluation period (“Post FVIII Prophylaxis to Last Visit”)
- The change from baseline (prior to BMN 270 infusion while receiving FVIII prophylaxis) in the annualized number of bleeding episodes irrespective of exogenous FVIII replacement therapy (annualized bleeding rate, ABR for all bleeds) in the efficacy evaluation period (“Post FVIII Prophylaxis to Last Visit”)
- The change from baseline (assuming no treatment for severe hemophilia A) in Haemo-QoL-A Total score, at Week 104 post-BMN 270 infusion
- The change from baseline (assuming no treatment for severe hemophilia A) in Haemo-QoL-A Physical Functioning domain score, at Week 104 post-BMN 270 infusion
- The change from baseline (assuming no treatment for severe hemophilia A) in Haemo-QoL-A Consequences of bleeding domain score, at Week 104 post-BMN 270 infusion
- The change from baseline (assuming no treatment for severe hemophilia A) in Haemo-QoL-A Role functioning domain score, at Week 104 post-BMN 270 infusion

The change from baseline in each subject’s FVIII activity is defined as the difference between the median of values obtained at Week 104 with the window defined in Appendix 20.1 and the baseline value, which will be imputed as 1 IU/dL for each subject.

The primary analysis of the change from baseline to Week 104 in FVIII activity will be a one-sample t-test on the mITT population. Missing values at Week 104 will be imputed using the imputation methods specified in Section 13.3.1.

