5.5 Baseline Value

The baseline values of the annualized utilization of exogenous FVIII replacement therapy and the annualized number of bleeding episodes are calculated using data during the specified period prior to enrollment as described in Section 13.3.

An imputed baseline FVIII activity of 1 IU/dL will be used for the change from baseline analysis since there will be no washout of severe hemophilia A subjects' usual FVIII prophylaxis (in order to avoid increasing the risk of bleeding) prior to BMN 270 infusion.

The baseline value of other assessments is defined as the last available measurement prior to the administration of study drug unless otherwise specified.

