13.3 Secondary Efficacy Endpoints

The first-ranked secondary efficacy endpoint is:

- The change from baseline (assuming no treatment for severe hemophilia A) in FVIII activity, as measured by chromogenic substrate assay, at Weeks 104 post-BMN 270 infusion

Each subject's FVIII activity level at Week 104 is defined as the median of the values obtained at Week 104 with the window defined in Appendix 20.1. The baseline value will be imputed as 1 IU/dL, since there will be no washout of severe hemophilia A subjects' usual FVIII prophylaxis (in order to avoid increasing the risk of bleeding) prior to BMN 270 infusion. Post-BMN 270 infusion values for FVIII activity will be excluded from analysis if obtained within 72 hours (or 3 calendar days if time is not available) since the last infusion of exogenous FVIII replacement therapy.

The second-ranked secondary efficacy endpoint is:

- The change from baseline (prior to BMN 270 infusion while receiving FVIII prophylaxis) in the annualized utilization (IU/kg/year) of exogenous FVIII replacement therapy in the efficacy evaluation period ("Post FVIII Prophylaxis to Last Visit")

The annualized utilization (IU/kg/year) of exogenous FVIII replacement therapy is defined as

$$\frac{\text{Sum of FVIII use (IU/kg) during calculation period}}{\text{Total number of days during the calculation period}} \times 365.25$$

The primary analyses for the annualized utilization (IU/kg/year) of exogenous FVIII replacement therapy will be performed on the Study 270-902 rollover subjects.

The calculation period in these formulas for the post-baseline value is:

- For the primary analysis, the efficacy evaluation period ("Post FVIII Prophylaxis to Last Visit") as defined in Section 13.1.
- For the supportive analyses, the efficacy periods as defined in Section 13.1.

The calculation period for the baseline value is defined in the following:

- For the primary analysis, the calculation period is approximately 6 months in the non-interventional study 270-902; i.e., the baseline values will be derived from the prospectively collected 6-month data in 270-902 up until the BMN 270 infusion date in 270-301.

Study 270-301 Statistical Analysis Plan

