	Week 100	Day 701	Days [687, 714]
	Week 104/EY	Day 730	Days [715, 743]
	Week 110	Day 772	Days [744, 792]
	Week 116	Day 814	Days [793, 835]
	Week 122	Day 856	Days [836, 877]
	Week 128	Day 898	Days [878, 919]
	Week 134	Day 940	Days [920, 961]
	Week 140	Day 982	Days [962, 1003]
	Week 146	Day 1024	Days [1004, 1045]
	Week 152	Day 1066	Days [1046, 1079]
	Week 156/EY	Day 1096	Days [1080, 1117]
	Week 162	Day 1138	Days [1118, 1159]
	Week 168	Day 1180	Days [1160, 1201]
	Week 174	Day 1222	Days [1202, 1243]
	Week 180	Day 1264	Days [1244, 1285]
	Week 186	Day 1306	Days [1286, 1327]
	Week 192	Day 1348	Days [1328, 1369]
	Week 198	Day 1390	Days [1370, 1411]
	Week 204	Day 1432	Days [1412, 1446]
	Week 208/EY	Day 1461	Days [1447, 1482]
	Week 214	Day 1503	Days [1483, 1524]
	Week 220	Day 1545	Days [1525, 1566]
	Week 226	Day 1587	Days [1567, 1608]
	Week 232	Day 1629	Days [1609, 1650]
	Week 238	Day 1671	Days [1651, 1692]
	Week 244	Day 1713	Days [1693, 1734]
	Week 250	Day 1755	Days [1735, 1776]
	Week 256	Day 1797	Days [1777, 1811]
	Week 260/EY	Day 1826	Days [1812, 1840]

^a Relative to the BMN 270 infusion day (Day 1)

^b Visit day is calculated as (visit date – date of infusion date + 1) if post infusion and (visit date – date of infusion date) if before infusion

^c Baseline visit value of FVIII activity is defined as the last available measurement prior to BMN 270 dosing excluding those within 72 hours after a FVIII infusion. Baseline visit value of other assessments is defined as the last available measurement prior to BMN 270 dosing.

^d For subjects enrolled from Study 270-902, the baseline value is derived from the period between the 270-902 enrollment day and the BMN 270 infusion day. For subjects not entering from 270-902, the baseline value is derived from the period between 12 months prior to 270-301 screening and the BMN 270 infusion day.

EY: end of year visit.

	
Study 270-301 Statistical Analysis Plan

---	--

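### The FVIII-activity MMRM treats baseline as a visit under an unstructured covariance, but the SAP fixes baseline at 1 IU/dL for everyone, so the model has no valid fit under that rule

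*SAP*

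**What the plan says.** Section 13.3.3 describes the alternative analysis of FVIII activity as an MMRM that "approach will also be used on the observed cases on the mITT population", with missing at random as the stated assumption. The structure is: "The model will include visit (every 4 weeks, from baseline to Week 104) as the only factor and will use an unstructured covariance matrix". The result is defined next: "The least squares (LS) mean change from baseline to Week 104 will be reported". The Synopsis describes the same model without naming the covariance.

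Three places fix the baseline as a constant:

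- Section 5.5: "An imputed baseline FVIII activity of 1 IU/dL will be used for the change from baseline analysis"
- Section 13.3, in the endpoint definition: "The baseline value will be imputed as 1 IU/dL"
- Synopsis, which takes the change from "the baseline value, which will be imputed as 1 IU/dL for each subject"

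Appendix 20.1 footnote c gives a second, measured baseline: "Baseline visit value of FVIII activity is defined as the last available measurement prior to BMN 270 dosing excluding those within 72 hours" of a FVIII infusion. Neither Section 5.5 nor the MMRM text says that this value replaces the imputed one for the change analysis.

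The MMRM text does not drop baseline from the repeated levels, does not make the response a change score, and names no other covariance in case the fit fails.

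**The concern.** In an MMRM with visit as the only factor and a reported contrast of Week 104 minus baseline, baseline is one of the repeated responses. An unstructured covariance needs a positive variance at every repeated level. A value that is 1 IU/dL for everyone has none, so the specification and the baseline rule cannot both be followed.

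Whoever programs the model must therefore depart from the text. Dropping the constant level keeps the endpoint. Substituting the measured pre-dose value changes it. The SAP does not say which to do, so the choice would be made with the data in hand.

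At stake is the only analysis of FVIII activity, the first-ranked secondary endpoint, that is explicitly based on missing at random. The other missing-data checks are the observed-case t-test, last observation carried forward, and setting missing values to 0 IU/dL.

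**Working it through.** The SAP attaches no figure to this MMRM, so there is none to reproduce. The nearest stated figure is the power for FVIII activity in Section 4.5: 130 subjects, effect size 0.6, two-sided 0.05, at least 95%. A noncentral-t calculation gives more than 0.9999, which agrees. That figure belongs to the t-test and is not in question.

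**Inputs**

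- Subjects: 134 treated, of whom 2 were HIV-positive (Synopsis). The mITT population is 134 − 2 = 132.
- Windows (Appendix 20.1): Weeks 1-4 to 49-52 give 13, leaving out the overlapping Weeks 23-26 window. Weeks 56 to 104 give 13. Total 26.
- Baseline: 1 IU/dL for each subject (Sections 5.5 and 13.3, Synopsis).

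**Covariance parameters**, k(k + 1)/2 for k visits:

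| Model | Visits | Parameters |
|---|---|---|
| As written, with baseline | 27 | 27 × 28 / 2 = 378 |
| Post-baseline windows only | 26 | 26 × 27 / 2 = 351 |

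Of the 378, 27 involve baseline: 1 variance and 26 covariances.

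**Rank.** If Y₀ = 1 for every subject, then Var(Y₀) = 0 and Cov(Y₀, Yⱼ) = 0 for all 26 other visits. The row and column are zero whatever the later values look like. Simulated complete data for 132 subjects (log-normal trajectories, assumed only for illustration) gave rank 26 of 27 and a smallest eigenvalue of 0.

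**Likelihood.** With complete data and visit as the only factor, −2 log REML is, up to a constant, (n − 1)[log|Σ| + tr(Σ⁻¹S)]. Let the baseline variance in Σ be v, with zero covariances. The observed baseline variance in S is 0, so baseline contributes only (n − 1) log v = 131 log v, which has no lower limit as v tends to 0. In the illustration:

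| v | −2 log REML |
|---|---|
| 1 | 21154.7 |
| 10⁻² | 20551.5 |
| 10⁻⁴ | 19948.2 |
| 10⁻⁸ | 18741.6 |
| 10⁻¹² | 17535.1 |

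Each hundredfold cut in v lowers the criterion by 131 × ln 100 = 603.3. The fit keeps improving as v goes to zero, so there is no positive-definite estimate.

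**Dropping the baseline level.** With FVIII activity minus 1 at the 26 post-baseline windows, the same data gave rank 26 of 26. The standard error of the Week 104 change was 1.97, equal to that of the Week 104 value itself. The constant carries no information, so removing it loses nothing.

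**Using the measured baseline.** Assuming 10% of subjects have a measured baseline at or above the lower limit of quantitation (3 IU/dL) and the rest are set to 0, the rank was 27 of 27, so the model can be fitted. The contrast is then taken from the mean measured baseline. With complete data it differs from the stated endpoint by 1 minus that mean. If every measured value were below 3 IU/dL and set to 0 under Section 5.6, the difference would be 1 − 0 = 1 IU/dL, but baseline would again be constant and the matrix singular.

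**The case against.** The best counter-argument is that the MMRM is confined to observed cases, and an imputed constant is not an observed case. Footnote c defines a measured baseline visit value in the same table that supplies the windows. On that reading the model is not exactly singular. This stands in part: a reader might infer that the model cannot be fitted on any reading, and the documents do not support that. It does not remove the conflict. Section 5.5 assigns the imputed value to change-from-baseline analyses because there was no washout of prophylaxis, and a measured baseline changes the quantity estimated.

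It can also be said that the practical consequence is small. The intended quantity is unambiguous (the Week 104 mean minus 1), and a sensible programmer would drop the constant level. That is fair and limits the weight of the point, but the text does not instruct it.

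Two further inferences are tempting. One is that 351 or 378 parameters for about 132 subjects shows that the fit would fail. It does not: subjects outnumber visits about fivefold (132 / 26 ≈ 5.1), and the illustration without baseline had full rank, although on complete data. Failure with realistic missingness has not been shown. The other is that sandwich standard errors make any simpler covariance safe. They protect the standard error only. Under missing at random, a misspecified covariance can bias the Week 104 mean itself.

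**Conclusion.** The point holds as an inconsistency within the SAP. With baseline at 1 IU/dL for each subject, the MMRM of Section 13.3.3 has a zero baseline row and column, rank 26 of 27, and no valid fit. This follows from the baseline rule alone and not from the simulated trajectories. The measured baseline generally escapes exact singularity, but the result would not be a sensitivity analysis of the stated endpoint. The missing covariance fallback is a secondary matter of good practice.

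The size is modest. One supportive analysis outside the nine-step hierarchy is affected. A reader might infer that the FVIII-activity conclusion is in doubt, or that the baseline was in fact switched. The documents support neither. The primary one-sample t-test does not use this model, and nothing shown records which baseline or covariance was fitted. The Haemo-QoL-A MMRM in the same section has a measured baseline that varies between subjects and does not share the problem.

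**What to change.** In Section 13.3.3 and the Synopsis, fit the FVIII-activity MMRM to the 26 post-baseline windows only, with FVIII activity minus 1 IU/dL as the response and no baseline level. Report the Week 104 LS mean as the change from baseline. State that the measured value in footnote c is not used in this model.

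Name in advance an ordered covariance fallback in case the unstructured matrix does not converge, for example heterogeneous Toeplitz and then heterogeneous AR(1). If sandwich standard errors accompany a fallback, say that they do not correct bias in the Week 104 mean from a misspecified structure under missing at random.

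The cost is a few lines of text and a small programming change. The Note to File states that the 2-year analysis was performed in January 2022, and its table of changes does not list this model. The practical step now is therefore to record which baseline and covariance were used, and to rerun this one analysis if they differ from the above.

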13.3.4 Correlation between FVIII Activity and Bleeding Risk

FVIII activity is widely acknowledged to be a key aspect of hemophilia A and a valuable indicator of patients' status, while annualized bleeding rate has been traditionally used as the primary clinical endpoint for replacement therapy. The correlation between FVIII activity level and bleeding risk has been researched, showing that increases in FVIII activity levels are predictably associated with a decreased number of annual bleeds ([den Uijl, 2011](#)). The following analyses will be performed to explore the relationship between measured FVIII activity and bleeding in this study.

- Using a cut-off of FVIII activity level, e.g., 40 IU/dL, each subject's data will be divided into 3 periods: baseline, from Week 5 to the first time reaching 40 IU/dL, and from the first time reaching 40 IU/dL to the end of efficacy period. For each period, the duration of the period, the number of bleeds, the ABR, and the change in ABR from baseline will be listed and summarized. ABR will also be estimated using negative binomial regression modelling number of treated bleeds vs period with period duration as the offset, repeated within subject. The analysis will be performed using various cut-off, such as 5, 15, 25, 30, 40 IU/dL.
- Based on the FVIII activity visit windows ([Appendix 20.1 Visit Windows](#)), median FVIII activity and total number of treated bleeds (defined in [Section 13.2](#)) will be calculated for each window for every subject. The total number of treated bleeds in each window will be plotted against the corresponding FVIII activity level to show the FVIII activity level around the time of bleeding. A negative binomial regression will be performed, modelling number of bleeds in each window vs. FVIII activity in the window, repeated within subject (the "repeated" term may be removed in case of convergence difficulty due to small sample size). The analysis will be done for FVIII activity measured by one-stage clotting assay and chromogenic assay separately. The same analyses will be conducted for treated joint bleeds.
- ABR will be summarized in subgroups of subjects determined by the FVIII activity levels as measured at Weeks 23-26, Weeks 49-52, Week 104, as well as by the peak FVIII activity levels.

